STUDY PROTOCOL AND STATISTICAL ANALYSIS PLAN

Official title: Furoscix in Heart Failure Patients with Diuretic Resistance

NCT number: NCT05528588

IRB Approved date: 07-22-24

Form A

IRB #

STU-2022-0768

PROTOCOL FORM / RESEARCH DESCRIPTION

If an item does not apply to your research project, indicate that the question is "**not applicable**" – do not leave sections blank

Click once on the highlighted entry in each box to provide your response. Click the item number/letter or word, if hyperlinked, for detailed instructions for that question. If your response requires inserting a table, picture, etc, you may need to first delete the box that surrounds the answer and then insert your table or other special document.

1. Purpose and objectives. *List the purpose and objectives:*

The purpose of this study is to assess the diuretic efficiency of subcutaneous furosemide (Furoscix) compared to oral diuretic therapy for patients post heart failure (HF) hospitalization and evaluate the impact of diuretic resistance as identified by the BAN-ADHF (Blood urea nitrogen, creatinine, Natriuretic Peptide levels, Atrial fibrillation, Diastolic blood pressure, Hypertension and Home diuretic dose, and Heart Failure hospitalization) risk score.

Key Outcomes:

1. Post-treatment urine output over 8 hours. This will be assessed in mL per mg of treatment (Furoscix vs. oral diuretic).
2. Post-treatment urine sodium. Urine sodium will be assessed hourly over 8 hours post-treatment.

Safety Outcome Measures:

1. Number of participants with post-intervention need for emergency department visit or hospitalization. The count of participants with post-intervention need for emergency department visit or hospitalization for worsening heart failure is assessed.

Goals: Successful completion of this project will establish proof of concept that Furoscix provides more effective post-hospitalization diuresis than the traditional oral dose in a diuretic resistance patient population. This study will provide pilot data to guide the design of larger studies involving a diuretic-resistant heart failure population.

2. Background.

- Describe past experimental and/or clinical findings leading to the formulation of your study.
- For research involving investigational drugs, describe the previously conducted animal and human studies.
- For research that involves FDA approved drugs or devices, describe the FDA approved uses of this drug/device in relation to your protocol.

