- Attach a copy of the approved labeling as a product package insert or from the Physician's Desk Reference.

You may reference sponsor's full protocol or grant application (section number and/or title) or if none, ensure background includes references.

Please respond to all components of this item, or clearly indicate which components are not applicable.

a. Background

Form A

IRB #

STU-2022-0768

Introduction

Heart failure is one of the leading causes of hospitalization in the United States, contributing to over 1 million emergency department visits and nearly 1 million hospitalizations for HF annually.¹ The estimated mean cost for HF was \$11,552 in 2014, totaling an estimated \$11 billion.² Thus, strategies to reduce the burden of acute care use for patients with heart failure are necessary. Acute decompensation of heart failure is characterized by volume overload and is primarily treated with intravenous diuretics. However, inefficient and ineffective diuresis both during hospitalization and in the post-discharge environment predispose patients to frequent readmission and a worse prognosis.³ Importantly, there is heterogeneity in patient response to intravenous diuresis, with an estimated 20-50% of patients having poor response to initial IV diuretic therapy.³ Patients who are resistant to intravenous diuresis have increased risk of re-hospitalization and mortality. Importantly, our group recently derived an integer-based risk score (BAN-ADHF score) to predict patients with low diuretic efficiency, with the research winning the NHLBI Heart Failure Data Challenge.^{4,5}

As part of patient's standard of care, they receive oral diuretics, including furosemide or torsemide, which are FDA approved for treating congestion and volume overload from heart failure. However, some patients are "resistant" to oral diuretics and have higher risk of repeat hospitalization. Therefore, purpose of this study is to evaluate treatment with subcutaneous furosemide (Furoscix) compared with oral diuretic therapy for patients with recent heart failure hospitalization either with or without diuretic resistance.

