Form A

IRB # STU-2022-0768

b. Current practice

[figure not shown]
After discharge, current practice is to transition patients back to a home oral diuretic regimen in hopes that this will provide sufficient diuresis to prevent re-hospitalization.

3. Study Design.

[figure not shown]
Describe the study design (e.g., single/double blind, parallel, crossover, etc.) Consider inserting a scheme to visually present the study design.

This will be a randomized, open-label pilot study of 70 patients with and without diuretic resistance who were recently admitted and discharged for acute decompensated heart failure with an oral diuretic regimen testing whether Furoscix is more effective at achieving post-discharge outpatient diuresis than standard of care.

Schema:

Visual description of the BAN-ADHF Score

Form A

IRB #

STU-2022-0768

4. Research Plan / Description of the Research Methods:**4.a. Provide a comprehensive narrative describing the research methods.**

- 1) Provide the order in which tests/procedures will be performed,
- 2) Provide the setting for these events and a description of the methods used to protect privacy during the study.
- 3) Provide the plan for data analysis (include as applicable the sample size calculation)

Please respond to all components of this item, or clearly indicate which components are not applicable.

Inclusion and Exclusion Criteria:

Eligibility criteria are shown in the following table:

Inclusion Criteria	Exclusion Criteria

 • English speaking patients discharged after ward hospitalization for acute decompensated heart failure • Able to be screened and enrolled within 14 days of discharge • Recent echocardiogram (6 months or less) • Discharged with diuretic therapy 	
 • Chronic kidney disease stage 5 (GFR<20) or End Stage Kidney Disease • Systolic blood pressure <100 • ICU hospitalization within 3 months • Inotrope use within last 3 months • Home inotropes • Electrolyte abnormalities on discharge • Inadequate data for BAN-ADHF score • Pregnant • Prior heart transplantation or left ventricular assist device • Low-output heart failure • Concurrent use of non-loop diuretic • Advanced liver disease • Severe malnutrition • Skin/Soft tissue condition precluding Furoscix • Inability to collect urine • Non-English-speaking patients

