If patients still meet all eligibility criteria and sign informed consent, they will undergo stratified randomization based on BAN-ADHF score (≥ 12 vs. < 12). Within each stratum, patients will be randomized in a 1:1 ratio (intervention: control) during the research visit. Patients will be informed via telephone prior to visit to not take home oral dose of diuretic on the day of the visit and will be instructed to hold any caffeine products such as coffee or any other drugs that could increase urine output on the day of the visit.

- **Intervention: Furoscix** – administration of subcutaneous furosemide (Furoscix) during study visit. It will be administered using the Furoscix Infusor. Per information from the Sponsor, "The Infusor is placed on the patient's abdomen for subcutaneous infusion. Furoscix is delivered subcutaneously through a small, 27-gauge, 6 mm needle. The Infusor is preprogramed to deliver 80 mg (10 mL) furosemide over 5 hours using a biphasic delivery profile of 30 mg furosemide (3.75 mL) over the first hour and 12.5 mg furosemide (1.56 mL) per hour over the subsequent 4 hours."
- **Control: Oral Diuretic** - administration of oral diuretic during study visit. Patients will bring their home prescription of oral diuretic and will take the oral formulation while in the visit. If the patient did not bring their home dose, an equivalent oral dose will be provided from the UT Southwestern Investigational Drug Service.

The intervention arm (Furoscix over 5 hours at 8 mg/mL) will be compared to a usual care group (home oral diuretic dose prescribed by discharge physician). Patients will be monitored for 8 hours in the Clinical Research Unit post-drug administration for clinical safety and to measure clinical response.

Other research procedures:

- Patients will be instructed to void immediately before dosing (pre-dose urine) and this sample will be discarded. After medication administration, urine from spontaneous voids during post-dose phases will be collected and recorded. Urine sodium measurements will be obtained at hourly intervals. Urine from each collection period must be refrigerated until the end of the collection period. Total volume of urine produced will be assessed over 8 hours post-study drug administration. 5 mL of each hourly urine sample will be sent for a urine sodium lab test in a yellow round bottom tube.

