- Collect approximately 10 mL of blood for a blood test to check patient's electrolytes. This will be done at the end of the research visit.
- Call participants in 7 days after their research visit to assess if patient has had a presentation to urgent care, emergency department, or is re-hospitalized for acute exacerbation in heart failure.

Compensation:

To account for a full day of research monitoring, patients will be compensated \$250 for their participation in the study with the UTSW ClinCard.

Data Safety and Monitoring:

Patient safety will be tracked over the study. For any adverse events (AE) that occur during their participation in the study, medical care will be provided and patients will be followed until resolution. See Form D for more details.

Form A

IRB #

STU-2022-0768

Privacy and Confidentiality:

To protect patient's privacy and confidentiality, we will ensure the consent process takes place in a private area and conduct research in secure areas where others will not have access to their PHI. All PHI collected during the study will be coded with a Subject ID using a randomized code. The key to the code will be kept on a password database in the research coordinator's locked office. Only authorized personnel listed on Form B will have access to the data. Any hard copy documents such as the signed consent form will be kept in the research coordinator's locked office.

Statistical Analysis:

This study will assess the primary outcomes of greater diuretic efficiency as measured by total urine output and urine sodium. As the Furoscix group will receive 80 mg of subcutaneous furosemide and the control group will take a home dose of oral diuretic, urine output will be normalized per mg of treatment administered. Differences in total urine produced will be compared between Furoscix versus oral diuretic groups. The urine sodium will be assessed hourly, and will be compared across the two groups.

As this study is a preliminary pilot study to assess the effect of Furoscix on diuretic efficacy, we have chosen a convenience sample of 70 patients to allow for a comparison between patients who receive Furoscix and those who do not receive Furoscix. The results of this trial will serve as a precursor for a larger, multicenter trial of Furoscix in patients with diuretic resistance.

4.b. List of the study intervention(s) being tested or evaluated under this protocol

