- Arrhythmia
- Nausea or vomiting

Less Likely, some may be Serious

In 100 people, approximately 2-20 may have:

- Deterioration in kidney function
- Increased uric acid and gout
- Urine bladder spasm
- Transient injection site pain
- Fever
- Restlessness

Rare and Serious

In 100 people, approximately 1 or less may have:

- Exacerbation of systemic lupus erythematosus
- Allergy to furosemide/Systemic hypersensitivity reactions
- Liver or kidney damage
- Tinnitus and hearing loss
- Aplastic anemia, thrombocytopenia, agranulocytosis
- Skin hypersensitivity reactions

Risks and side effects related to Oral Diuretic Therapy:

Likely, some may be Serious

In 100 people, approximately 21-100 may have:

- Dehydration
- Electrolyte depletion, including low potassium (hypokalemia), low sodium (hyponatremia), low magnesium (hypomagnesemia), low calcium (hypocalcemia).
- Dry mouth
- Thirst
- Weakness
- Muscle pains or cramps
- Low blood pressure
- High heart rate
- Dizziness

Less Likely, some may be Serious

In 100 people, approximately 2-20 may have:

- Deterioration in kidney function or an acute kidney injury
- Increased uric acid and gout
- Urine bladder spasm

Rare and Serious

In 100 people, approximately 1 or less may have:

- Exacerbation of systemic lupus erythematosus
- Allergy to furosemide or torsemide/Systemic hypersensitivity reactions
- Liver or kidney damage
- Tinnitus and hearing loss
- Aplastic anemia (bone marrow failure), thrombocytopenia (low blood platelet count), agranulocytosis (low white blood cell count)
- Skin hypersensitivity reactions such as skin rash

Form A

IRB #

STU-2022-0768

Furoscix is a specific subcutaneous formulation of furosemide. Patients are required to be taking home diuretics as eligibility criteria; therefore we anticipate very few side effects associated with the medication. Skin reactions may occur with administration of Furoscix, although this is a rare side effect. Patients will be monitored for 8 hours post medication administration, with a serum potassium check performed after the study visit to ensure stable serum electrolytes.

b. Where appropriate, discuss provisions for ensuring necessary medical or professional intervention in the event of adverse events, or unanticipated problems involving subjects.

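### The mL-per-mg outcome has no between-drug conversion, so the control mean and the Furoscix contrast shift with the share of controls taking torsemide unless the drugs are equipotent per mg

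*Combined protocol and SAP*

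**What the plan says.** Section 1 lists 8-hour urine output first among the key outcomes, in mL per mg of treatment. Statistical Analysis in section 4.a repeats this: "urine output will be normalized per mg of treatment administered". The reason given there is that one arm gets 80 mg of subcutaneous furosemide and the other a home dose. That reason covers different doses, not different drugs.

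On which drug the controls take:

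- Inclusion criteria, section 4.a: "Discharged with diuretic therapy". No drug is specified. The exclusion list rules out patients who also take a diuretic outside the loop class, but does not limit loop diuretics to furosemide.
- Control arm, section 4.a: "Patients will bring their home prescription of oral diuretic and will take the oral formulation while in the visit".
- Background, section 2.a, on standard of care: "they receive oral diuretics, including furosemide or torsemide".
- Risks, section 5.a: the Furoscix list has "Allergy to furosemide/Systemic hypersensitivity reactions", while the oral-therapy list has "Allergy to furosemide or torsemide/Systemic hypersensitivity reactions". The protocol therefore foresees torsemide in the oral arm.

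On allocation, section 4.a says that "they will undergo stratified randomization based on BAN-ADHF score"; home drug is not a stratification factor. The supplied text contains no conversion factor, no furosemide-equivalent denominator, and no adjustment or analysis by drug.

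**The concern.** Dividing by milligrams puts patients on one scale only if a milligram means the same thing for each of them. In the Furoscix arm it does, because everyone receives furosemide. In the control arm the denominator may mix furosemide and torsemide. If the drugs differ in potency per mg, a torsemide patient with the same effective dose and the same urine volume gets a different mL/mg value.

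Randomization does not cancel this. Even with home drug perfectly balanced between arms, the Furoscix denominator ignores home drug and the control denominator depends on it. The computed contrast would then partly measure prescribing habits at discharge. The study is meant to give proof of concept and pilot data for a larger trial, so a distorted contrast would be carried into that design. The study is also open-label, so a conversion chosen after outcomes are seen could influence the result.

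**Working it through.** **Inputs from the documents.** The Furoscix dose is 80 mg, which agrees with its stated profile: 30 + 4 × 12.5 = 80 mg. The sample is 70, randomized 1:1, so about 35 per arm. It is a convenience sample with no alpha, power or SD stated, so there is no sample-size figure to reproduce.

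**Assumptions, not in the documents.** Torsemide is r times as potent per mg as furosemide. A share s of controls take torsemide and the rest take furosemide. All controls take the same furosemide-equivalent dose D and pass the same volume V.

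**Formula.** A furosemide control contributes V/D. A torsemide control takes D/r mg and contributes rV/D. Hence

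control mean = (V/D)[(1 − s) + s·r] = (V/D)·m, with m = 1 + s(r − 1).

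If the true Furoscix/control ratio in furosemide-equivalent mg is 1.00, the ratio computed without conversion is 1/m.

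**Example (illustrative V = 2000 mL, D = 80 mg, r = 2, s = 25%).** Furoscix: 2000/80 = 25.0 mL/mg. Furosemide controls: 25.0. Torsemide controls: 2000/40 = 50.0. Control mean: 0.75 × 25.0 + 0.25 × 50.0 = 31.25. Computed ratio: 25.0/31.25 = 0.80, with no true difference. After conversion, 40 × 2 = 80 mg, every control is at 25.0 and the ratio is 1.00 for any s.

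**Range: control multiplier m, then computed ratio 1/m**

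| r | s = 10% | s = 25% | s = 50% |
|---|---|---|---|
| 0.5 | 0.95; 1.05 | 0.875; 1.14 | 0.75; 1.33 |
| 1 | 1.00; 1.00 | 1.00; 1.00 | 1.00; 1.00 |
| 2 | 1.10; 0.91 | 1.25; 0.80 | 1.50; 0.67 |
| 3 | 1.20; 0.83 | 1.50; 0.67 | 2.00; 0.50 |
| 4 | 1.30; 0.77 | 1.75; 0.57 | 2.50; 0.40 |

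The dependence on s vanishes only at r = 1. The bias runs against Furoscix for r > 1 and in its favour for r < 1.

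**When a real advantage would be hidden.** With a true 30% volume advantage for Furoscix, the computed ratio is 1.3/m. At r = 2 this is 1.3/1.25 = 1.04 for s = 25% and 1.3/1.50 = 0.87 for s = 50%. It falls below 1 once s exceeds 0.3/(r − 1): 60% at r = 1.5, 30% at r = 2, 15% at r = 3, 10% at r = 4.

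**Chance of a spurious finding.** The plan states no test. For illustration, take a two-sided z-test at 0.05, 35 per arm, a within-drug coefficient of variation of 50% and no true difference. The probability of declaring a difference is 5% at r = 1. At r = 2 it is 35% for s = 25% and 80% for s = 50%.

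**The case against.** The strongest objection is about materiality. The documents show that torsemide is possible, not that it is common, and give no potency ratio. At r = 1 or s = 0 nothing is wrong, and at s = 5%, r = 2 the multiplier is only 1.05 (ratio 0.95). This stands as a limit on any claim about size, but it does not supply the missing rule.

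The equal-dose, equal-volume model is also a simplification, since controls take individual home doses. If torsemide users passed half the volume per equivalent mg, then at s = 50% and r = 2 the unconverted mean would be 0.5 + 0.5 × 0.5 × 2 = 1.00 against a converted mean of 0.5 + 0.25 = 0.75. The multiplier is 1.33, not 1.50: the size changes and the direction does not.

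Two passages might seem to fill the gap. Section 4.a promises an equivalent oral dose to a control who arrives without medication, but that concerns replacement supply and gives no factor or analysis rule. Home diuretic dose is a component of the BAN-ADHF score, and the score figure is not shown in the supplied text. Any dose convention inside the score is not linked to the outcome denominator.

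Finally, conversion can do harm if the factor is wrong. Using factor 2 when r = 1 gives a control multiplier of 0.875 (s = 25%) or 0.75 (s = 50%), which is a spurious ratio of 1.14 or 1.33. This stands, and is the reason for the sensitivity range and for reporting unnormalized volume.

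**Conclusion.** The concern holds. The plan sets a per-milligram rule, admits more than one drug to one arm only, and gives no common unit. That much rests on the text alone. The size and sign depend on r and s, which the documents do not give. Across the values tabulated, the computed ratio under no true difference runs from 0.40 to 1.33, and it is exactly 1.00 when the drugs are equipotent.

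Only the mL/mg outcome is affected. Urine sodium is not stated to be normalized, and the plan's sentence on comparing total urine can be read as an unnormalized comparison, which would also be unaffected.

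**What to change.** In Statistical Analysis, express the denominator in furosemide-equivalent mg, using one oral-to-oral factor per drug, fixed and sourced before outcome data are seen. Apply no conversion across routes: the Furoscix denominator stays at 80 mg, so the route difference under study is not absorbed. Then add:

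1. A sensitivity analysis over a stated range of the factor.
2. A sensitivity analysis restricted, in both arms, to patients whose pre-randomization home drug is furosemide.
3. Unnormalized 8-hour urine volume by arm, reported alongside.

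Record home drug and dose in both arms from the medication assessment already planned before randomization. For each control, record the drug and mg actually taken, since replacement supply might differ from the home drug.

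The cost is a sentence or two, a small conversion table and a data field. Recording mg is already implied by the outcome; recording the drug taken is not stated. No extra visits or patients are needed.

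There are limits. With factor f when the true ratio is r, the residual multiplier is 1 + s(r/f − 1). For f = 2 and r = 3 this is 1.125 (s = 25%) or 1.25 (s = 50%), against 1.50 or 2.00 unconverted. The furosemide-only analysis would have fewer than 70 patients if any take another drug, and is not stratified by home drug. Conversion also does not remove the separate dependence of mL/mg on a varying home dose set against a fixed 80 mg.

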Intervention, Setting, and Design: We are recruiting patients from UTSW and Parkland. All of the research procedures in this study will take place at the Clinical Research Unit in the Aston Building at UT Southwestern Medical Center. This will be a randomized, open-label pilot study of 70 patients with and without diuretic resistance who were recently admitted and discharged for acute decompensated heart failure with an oral diuretic regimen testing whether Furoscix is more effective at achieving post-discharge outpatient diuresis than oral diuretics. Diuretic resistance will be identified using the BAN-ADHF (Blood urea nitrogen, creatinine, Natriuretic Peptide levels, Atrial fibrillation, Diastolic blood pressure, Hypertension and Home diuretic dose, and Heart Failure hospitalization) score which has been integrated into the electronic health record. The score is integer-based with a score of ≥ 12 indicating diuretic resistance with high likelihood of poor outcomes.

Screening:

- We are requesting a partial HIPAA waiver to review electronic health records and confirm their eligibility in the study. Pre-screening will occur through the electronic health record to evaluate for inclusion and exclusion criteria and to assess if women of child-bearing potential have a pregnancy test to confirm they are not pregnant. Lab testing will be reviewed. These include review of urine drug screen, alcohol screen (if clinically indicated), NT-proBNP, creatinine clearance.
- BAN-ADHF score will be calculated.

Form A

IRB #

STU-2022-0768

- After patients are screened, patients will be approached for potential participation. If patients are interested, they will be scheduled for an in-person randomization visit optimally within 1-7 days of hospital discharge, although patients will be eligible up to 14 days after discharge.
- At the research appointment, patients will be asked if they are interested in voluntarily participating in this study.

Research Visit:

Pre-Randomization:

- Confirm eligibility
- Obtain informed consent
- Physical exam including vital signs assessment.
- Prior and concomitant medication assessment.

Randomization:

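### Randomisation is stratified on BAN-ADHF, which the protocol presents as a predictor of diuretic efficiency, but the stated two-group analysis does not use the score

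*Combined protocol and SAP*

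**What the plan says.** The Statistical Analysis paragraphs of Section 4.a of the combined protocol and SAP describe the whole comparison. For urine output: "Differences in total urine produced will be compared between Furoscix versus oral diuretic groups", on a scale where "urine output will be normalized per mg of treatment administered". For sodium: "The urine sodium will be assessed hourly, and will be compared across the two groups". No test, model, covariate or stratum term is named.

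Three other places bear on this:

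- Section 4.a, Randomization: if patients remain eligible and consent, "they will undergo stratified randomization based on BAN-ADHF score", split at 12, and within each stratum "patients will be randomized in a 1:1 ratio (intervention: control) during the research visit".
- Section 2.a, Background: the score was derived "to predict patients with low diuretic efficiency". The Statistical Analysis text names diuretic efficiency as what the primary outcomes measure.
- Section 4.a, Screening and the eligibility table: the score is calculated before randomisation, and patients without enough data for it are excluded. It should therefore be complete for every randomised patient.

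On sample size the plan says "we have chosen a convenience sample of 70 patients to allow for a comparison between patients who receive Furoscix". It gives no alpha, power, effect size or standard deviation.

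**The concern.** The protocol identifies a baseline variable that it expects to predict the primary outcome, collects it on everyone and stratifies on it, but states an analysis in which it plays no part.

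Stratifying on a prognostic factor makes the arms alike on that factor, so the treatment difference varies less from trial to trial than under simple randomisation. A plain two-sample analysis does not register this. It leaves the between-stratum spread in the residual variance and so reports a standard error larger than the real one. The interval is then too wide and the test rejects less often than its nominal level. Using the score itself, and not only its split at 12, can also reduce the real variability.

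The results of this pilot are meant to inform a larger multicentre trial, so the width of its intervals is one of its main products.

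**Working it through.** **Inputs.** From Section 4.a: 70 patients, 1:1, hence 35 per arm; stratified at BAN-ADHF 12. Assumed, because the documents do not state them: two-sided alpha 0.05, outcome SD of 1 within arm (standardised), a true difference of 0.5 SD, no dropout, score R² of 0.10, 0.20 or 0.30, a normally distributed score, and half the patients in each stratum. There is no power calculation in the plan to reproduce, since 70 is a convenience sample.

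**Standard errors.**

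1. Reported by the plain comparison: √(4/70) = 0.239 SD. The score's variation stays in the residual, so this does not depend on R².
2. Actual, under stratified randomisation: √[(4/70)(1 − c·R²)], where c is the share of the score's explained variance that the split captures. With a proportion p of patients above the cut, c = φ(z)²/[p(1 − p)], where z is the cut-point on the standard normal scale. For p = 0.5, c = 0.159/0.25 = 0.637. A model with the stratum term reports this standard error.
3. Model with the continuous score: √[(4/70)(1 − R²)], ignoring the small cost of one degree of freedom.

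For R² = 0.20, the actual value is √(0.0571 × 0.873) = 0.223, and with the continuous score √(0.0571 × 0.80) = 0.214.

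**Error rate and power.**

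- Type I error of the plain test: 2Φ(−1.96 × reported/actual).
- Power of the plain test: Φ[(0.5 − 1.995 × 0.239)/actual].
- Power of each model: Φ(0.5/SE − 1.995).
- 1.995 is the t critical value on 68 degrees of freedom.

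| Score R² | Actual SE, plain or stratum | SE, continuous score | Reported/actual, plain | Type I error, plain | Power: plain / stratum / continuous |
|---|---|---|---|---|---|
| 0.10 | 0.231 | 0.227 | 1.03 | 4.3% | 54% / 57% / 58% |
| 0.20 | 0.223 | 0.214 | 1.07 | 3.6% | 54% / 60% / 63% |
| 0.30 | 0.215 | 0.200 | 1.11 | 2.9% | 54% / 63% / 69% |

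**Check by simulation.** I ran 20,000 trials per scenario, with a median split and permuted blocks of 4 (the block size is also an assumption). Type I error of the plain test was 4.1%, 3.6% and 3.0% at R² of 0.10, 0.20 and 0.30. Power was 54/56/58%, 54/59/63% and 54/63/69%. Both models held about 5% type I error. At R² = 0 all three analyses had 54% power, so the cost of including a useless score is negligible.

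**Where the gain comes from.** At R² = 0.20 the plain analysis reports 0.239 when the real value is 0.223. The stratum term corrects the reported figure and leaves the estimate's real variability unchanged. The continuous score lowers the real value further, to 0.214, a reduction of about 4% (0.214/0.223 = 0.96). At R² = 0.30 the further reduction is 7% (0.200/0.215 = 0.93).

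**Sensitivity to the split.** The documents do not say what share of patients will score 12 or more. With 20% in one stratum, c = 0.0784/0.16 = 0.49, and the plain test's type I error is 3.9% at R² = 0.20 and 3.4% at R² = 0.30. The direction is the same and the size somewhat smaller.

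**The per-mg scale.** Home diuretic dose is a component of BAN-ADHF and also the denominator of the control arm's outcome, whereas the Furoscix denominator is fixed at 80 mg. The slope on the score and the residual spread may therefore differ by arm, so a common-slope model with an ordinary standard error is not fully safe for mL per mg.

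**The case against.** The strongest reply is that nothing becomes invalid. The plain comparison is unbiased under randomisation, ignoring the stratum errs on the conservative side, and this is a self-described pilot with no precision target. That stands, and it limits the point to an efficiency improvement. It does not remove the point, because the data are already collected and the change costs only text.

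A second reply is that the plan does not choose an unadjusted analysis; it names no method. That is also fair. An adjusted model is compatible with the wording, but then the wording has to say so before the data are seen.

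A reader might infer more than the documents support:

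- **That days since discharge should also be a covariate.** Visits are to be "optimally within 1-7 days of hospital discharge, although patients will be eligible up to 14 days after discharge", but no reason is given, and nothing shows that timing predicts 8-hour urine output or sodium.
- **That home oral dose should be added.** It is already inside the score and is the control arm's denominator.
- **That adjustment is worth a stated number of extra patients.** Converting the narrower reported interval into patients overstates the gain, because much of the narrowing corrects an inflated standard error.
- **That the outcomes should change to total volume and total sodium excreted.** That would be a different question from the one the plan poses, and precision alone does not justify it.

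**Conclusion.** The point holds as a modest improvement. The analysis should reflect the factor on which randomisation is stratified, and the protocol's own account of the score is reason to expect a benefit. With score R² of 0.20 to 0.30, the plain analysis overstates the standard error by 7 to 11%, runs at about 3% type I error, and gives up roughly 6 to 9 percentage points of power against a model with the stratum, or 9 to 15 points against one with the continuous score, for a 0.5 SD effect. At R² of 0.10 the gain is 3 to 4 points.

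These sizes rest on assumed values for R², the effect size and the stratum split. The direction needs only that the score is prognostic. The documents do not support saying that the planned comparison is biased or would produce false positive findings.

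**What to change.** In the Statistical Analysis part of Section 4.a, state that each primary outcome, as now defined, will be compared between arms with one pre-specified linear model containing treatment and BAN-ADHF: the ≥12 stratum at minimum, preferably the continuous score. For sodium, the same terms enter whatever model is specified for the hourly values. Report the adjusted difference with a 95% CI, and the unadjusted difference as a sensitivity analysis.

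For the mL-per-mg outcome, add either a robust standard error or a centred score-by-arm term, chosen in advance, because home dose enters both the score and the control denominator.

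The cost is SAP wording and one or two degrees of freedom. No new data, visits or patients are needed.
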